9.3 Serious Adverse Event Reporting – Procedures for Investigators

Initial Reports

All SAEs occurring from the time of treatment assignment (Phase 1) or randomization (Phase 2) until 30 days following the last administration of study drug, or the subject initiates alternative antineoplastic therapy that is not permitted during this study, must be reported to Medpace Clinical Safety within 24 hours of the knowledge of the occurrence (this refers to any adverse event that meets any of the aforementioned serious criteria). All SAEs that the Investigator considers related to study drug occurring after the 30-day follow-up period must be reported to the Sponsor. The Principal Investigator must notify the IRB and IBC of the SAE in writing (electronic transmissions acceptable), in accordance with IRB and IBC requirements.

To report the SAE, complete the SAE form electronically in the electronic data capture (EDC) system for the study. When the form is completed, Medpace Safety personnel will be notified electronically and will retrieve the form. If the event meets serious criteria and it is not possible to access the EDC, send an email to Medpace Safety at [contact]

or call the Medpace SAE hotline (phone number listed below), and fax the completed paper SAE form to Medpace (fax number listed below) within 24 hours of awareness. When the EDC system becomes available, the SAE information must be entered within 24 hours of the system becoming available.

Safety Contact Information: Medpace Clinical Safety

Medpace SAE hotline – USA:

[contact], ext. 2999 or [contact], ext. 2999

[contact] or [contact]

e-mail: [contact]

Follow-up Reports

The Investigator must continue to follow the subject until the SAE has subsided or until the condition becomes chronic in nature, stabilizes (in the case of persistent impairment), or the subject dies.

Within 24 hours of receipt of follow-up information, the Investigator must update the SAE form electronically in the EDC system for the study and submit any supporting documentation (eg, subject discharge summary or autopsy reports) to Medpace Clinical Safety via fax or e-mail. If it is not possible to access the EDC system, refer to the procedures outlined above for initial reporting of SAEs.

9.4 Pregnancy Reporting

If the subject becomes pregnant during the study or within 30 days of discontinuing study drug, the Investigator should report the pregnancy to Medpace Clinical Safety within 24 hours of being notified. Medpace Clinical Safety will then forward the Exposure *In Utero* form to the Investigator for completion.

A subject becoming pregnant while on study drug will immediately be withdrawn from the study and early termination study procedures will be performed.

The subject should be followed by the Investigator until completion of the pregnancy. If the pregnancy ends for any reason before the anticipated date, the Investigator should notify Medpace Clinical Safety. At the completion of the pregnancy, the Investigator will document the outcome of the pregnancy. If the outcome of the pregnancy meets the criteria for immediate classification as an SAE (ie, postpartum complication, spontaneous abortion, stillbirth, neonatal death, or congenital anomaly), the Investigator should follow the procedures for reporting an SAE.

9.5 Expedited Reporting

The Sponsor will report all relevant information about suspected unexpected serious adverse reactions that are fatal or life-threatening as soon as possible to the FDA and other applicable regulatory authorities as applicable, and in any case no later than 7 days after knowledge by the Sponsor of such a case, and that relevant follow-up information will subsequently be communicated within an additional 8 days.

All other suspected unexpected serious adverse reactions will be reported to the FDA and other applicable regulatory authorities as soon as possible but within a maximum of 15 days of first knowledge by the Sponsor.

The Sponsor will also inform all Investigators as required.

9.6 Definition of an Overdose for This Protocol and Reporting of Overdose to the Sponsor

For purposes of this study, an overdose is defined as the accidental or intentional administration of any dose of a product that is considered both excessive and medically important. All occurrences of overdose must be reported as an SAE (see [Section 9.3](#) for reporting details).

There has been no clinical experience with overdosage of CRS-207, epacadostat, or pembrolizumab. Treatment of overdosage should consist of general supportive measures.

9.7 Clinical Laboratory Evaluations

The Investigator may use clinical judgment when determining the clinical significance of laboratory parameter findings throughout the study. The Study Medical Monitor may, depending on study criteria, be consulted before enrollment about a potential subject with abnormal laboratory values that are not considered clinically significant. Additional tests may be performed or repeated as clinically indicated.

9.7.1 Chemistry and Hematology

A comprehensive serum chemistry and hematology panel will be performed as indicated in the [Schedule of Events](#); required analytes for this panel are listed in [Appendix A](#), Clinical Laboratory Analytes. The chemistry and hematology panel will be performed by the site's local laboratory. Fasting is not required unless clinically indicated.

9.7.2 Liver Function Tests

LFTs will be performed as indicated in the [Schedule of Events](#); required analytes for this panel are listed in [Appendix A](#), Clinical Laboratory Analytes. If LFTs are found to be abnormal, frequency of monitoring should be increased to once per week until LFTs have resolved to baseline or corticosteroid treatment has begun, at which time chemistry test monitoring will be performed according to institutional standards or approximately weekly, whichever is shorter. Liver function does not need to be monitored once per week indefinitely for persistent low-grade abnormalities. Appropriate liver function monitoring intervals should be discussed with the Study Medical Monitor. LFTs will be performed by the site's local laboratory.

9.7.2.1 Potential Drug-Induced Liver Injury (Hy's Law)

Wherever possible, timely confirmation of initial liver-related laboratory abnormalities should occur prior to the reporting of a potential drug-induced liver injury (DILI) event (also known as Hy's Law). All occurrences of potential DILIs, meeting the defined criteria, must be reported as SAEs (see [Section 9.3](#) for reporting details).

Potential DILI is defined as meeting all of the following criteria:

- Aminotransferase (ALT or AST) elevation $\geq 3 \times$ ULN
- Total bilirubin $\geq 2 \times$ ULN, without initial findings of cholestasis (elevated serum alkaline phosphatase)
- ALP < 2 ULN

- No other immediately apparent possible causes of aminotransferase elevation and hyperbilirubinemia, including, but not limited to, viral hepatitis, pre-existing chronic or acute liver disease, or the administration of other drugs known to be hepatotoxic.

9.7.3 Urinalysis

Urinalysis will be performed as indicated in the [Schedule of Events](#); required analytes for this panel are listed in [Appendix A](#), Clinical Laboratory Analytes. Urinalysis will be analyzed by the site's local laboratory.

9.7.4 Coagulation

A coagulation panel will be performed as indicated in the [Schedule of Events](#); required analytes for this panel are listed in [Appendix A](#), Clinical Laboratory Analytes. If a coumarin-based anticoagulant is given, INR should be monitored as described in the [Schedule of Events](#). Coagulation panel will be analyzed by the site's local laboratory.

9.7.5 Endocrine and Thyroid Function Testing

Endocrine and thyroid function testing will be performed as indicated in the [Schedule of Events](#); required analytes for this panel are listed in [Appendix A](#), Clinical Laboratory Analytes. Endocrine function testing will not be collected for CRS-207 monotherapy dosed subjects. The endocrine and thyroid function testing will be performed by the site's local laboratory.

9.7.6 Pregnancy Testing

Pregnancy testing will be performed as indicated in the [Schedule of Events](#). A serum pregnancy test is required for women of childbearing potential only and must be performed and confirmed negative prior to the first dose of study drug. Urine pregnancy tests for women of childbearing potential should be repeated and confirmed negative on Day 1 of each cycle and at the Safety Follow-up Visit. Serum testing may be conducted if urine pregnancy testing is unavailable. Serum and/or urine pregnancy test may be conducted up to 3 days before each dosing cycle where indicated. Pregnancy testing will be performed by the site's local laboratory.

If the serum pregnancy test is negative after a urine test was positive, the Investigator will assess the potential benefit/risk to the subject and determine whether it is in the subject's best interest to resume study drug and continue participation in the study.

9.7.7 Additional Laboratory Assessments

CD4 count, HLA-typing (low resolution), and a virology screen ([Appendix A](#)) will be performed once during the study as indicated in the [Schedule of Events](#).

9.7.8 Shedding and Clearance of CRS-207

During Phase 1 and the Safety Run-in of Phase 2 at select US centers only, urine, rectal swab, oral swab, and whole blood will be collected from subjects pre-dose, and at 6 hours, 18 to 24 hours, and Day 7 post-CRS-207 infusion on Cycle 1 and Cycle 2. **The central line MAY NOT be used for obtaining blood samples.** Additional assessments will be performed if results are positive for CRS-207 at the Day 7 time point. Samples will be sent to the central laboratory. Additional details on sample collection, processing, and shipping are provided in the Laboratory Manual.

9.7.9 Blood Cultures for CRS-207 Surveillance

Blood samples will be obtained from subject's peripheral vein and from the central line port, if applicable, at the EOT visit [REDACTED]

9.8 Vital Signs, Weight, and Height

Vital signs, including seated BP, pulse rate, respiratory rate, and temperature, will be performed for all Treatment Arms as indicated in the Schedule of Events. Pulse oximetry will be measured if clinically indicated. Vital signs will additionally be monitored during infusion, per the CRS-207 infusion guidelines ([Section 5.5.2.1](#)).

Weight will be taken on Day 1 of each cycle. Height is required at screening only.

9.9 Physical Examinations

9.9.1 Comprehensive Physical Examination

Physical examinations must be performed by a medically qualified individual such as a licensed Physician, Physician's Assistant, or an advanced Registered Nurse Practitioner, as local law permits. The comprehensive physical examination will include the following organ or body system assessments: skin; head, eyes, ears, nose, and throat; thyroid; lungs; cardiovascular system; abdomen (liver and spleen); extremities; lymph nodes; and a brief neurological examination. Before the first dose of study drug, clinically significant abnormal findings should be recorded as medical history. After the first dose of study treatment, new clinically significant abnormal findings should be recorded as adverse events.

9.9.2 Symptom-Directed Physical Examination

For visits that do not require a full physical examination per the [Schedule of Events](#), the Investigator or medically qualified designee will perform a symptom-directed evaluation as clinically indicated. The targeted physical examination will include assessment(s) of the body systems or organs, as indicated by subject symptoms, adverse events, or other findings. New clinically significant abnormal findings should be recorded as adverse events.

9.10 ECOG Performance Status

The ECOG Scale of Performance Status is recognized as a standard tool to measure disease impact on daily living activities. The ECOG scale will be used by site personnel to determine eligibility and characterize a subject's level of functioning (self-care, daily activity, and basic physical ability) as indicated in the [Schedule of Events](#).

9.11 Electrocardiograms

ECG assessments will be conducted as indicated in the [Schedule of Events](#). All 12-lead ECGs will be performed in triplicate with the subject in a recumbent or semi-recumbent position after 5 minutes of rest. In order not to confound interpretation of the ECG, if anti-emetics or other prophylactic agents are given then these should be given after the pre-dose ECG rather than before.

Clinically significant abnormal findings after signing informed consent should be recorded as an adverse event. The 12-lead ECGs will be interpreted by the Investigator at the site and will be used for immediate subject management. The decision to include or exclude a subject or withdraw a subject from the study based on an ECG flagged as "Abnormal, Clinically Significant" is the responsibility of the Investigator, in consultation with the Study Medical Monitor, as appropriate.

10 STATISTICS

10.1 Analysis Populations

The Full Analysis Set (FAS) includes all subjects who received at least 1 dose of study drug. FAS analyses will be conducted on the basis of the randomized treatment. All efficacy analyses will be assessed using the FAS.

A Per-Protocol Set (PPS) will also be used to analyze efficacy endpoints and will be based on study drug exposure (compliance and/or time on study drug) and major protocol deviations. The criteria for inclusion in the PPS will be finalized and documented in the statistical analysis plan (SAP) prior to database lock.

The Safety Set (SAF) includes all randomized subjects who received at least 1 dose of study drug. The SAF will be conducted on the basis of the actual treatment received. All safety analyses will be assessed using the SAF.

10.2 Statistical Methods

All statistical analyses will be performed using SAS[®] version 9 or higher.

Phase 1 and Phase 2 will be analyzed separately. Data will be summarized descriptively for Phase 1 by cohort and overall and Phase 2 by Arm and overall. Descriptive summaries for categorical variables will include counts and percentages. Descriptive summaries for continuous variables will include means, medians, standard deviations and minimum and maximum values. Descriptive summaries of time to event data will include median, 25th and 75th percentiles and standard error. Graphical summaries of the data may be presented. All data will be listed for all subjects.

The effects of noncompliance, time to first dose, treatment discontinuations, premature withdrawal from study and covariates will be assessed to determine the impact on the general applicability of results from this study. Further details of the analysis, including the handling of missing data, transformations and other data handling procedures will be provided in the SAP. Exploratory analyses of the data will be conducted as deemed appropriate.

10.2.1 Analysis of Efficacy

All efficacy analyses will be conducted on both the FAS and PPS.

10.2.1.1 Objective Response Rate

Objective response rate (ORR) is defined as the proportion of subjects with PR or CR according to mRECIST. Subjects who discontinue prior to post-baseline tumor assessments will be considered as non-responders.

The primary definition for objective disease response is based on mRECIST. Analyses will be performed separately using objective disease responses definitions based on the mRECIST, RECIST v1.1, and GCIG CA-125 criteria. Analysis repeated for RECIST v1.1 and GCIG CA-125 are considered supportive.

Progressive serial elevation of serum CA-125 will be used to determine CA-125 response. Guidelines for using CA-125 response have been developed. Refer to [Appendix C](#) for Gynecological Cancer Intergroup Definitions for Response and Progression Based on CA-125 Quick Reference. Subjects should have a pre-treatment CA-125 of at least twice the ULN in order

to be considered for CA-125 response. Subjects are not evaluable by CA-125 if they have received mouse antibodies or if there has been medical and/or surgical interference with their peritoneum or pleura during the previous 28 days. In those subjects considered evaluable by CA-125, a CA-125 response would be obtained the moment the CA-125 is reduced by 50% and this should be confirmed with a consecutive CA-125 assessment not earlier than 28 days after the previous one, with however the date of the first 50% reduction to be the reference date for the CA-125 response.

For each cohort in Phase 1 and each Arm in Phase 2, objective disease responses will be summarized by response at each visit and best objective response. The number of subjects with disease control, defined as subjects with best objective response of CR, PR or SD, will also be summarized.

For expansion to the second stage in Phase 2, ORR and PFS will be assessed using mRECIST as the primary measure for assessment.

10.2.1.2 Progression-Free Survival

PFS is defined as the time from the date of first dose to PD or death due to any cause. Subjects who do not experience PD and do not die on or before the data cut-off date will be censored at the time of last tumor assessment or data cut-off date, whichever is earlier. Subjects who do not experience PD and start new systemic therapy will be censored at the time the new systemic therapy was begun or the data cut-off date, whichever is earlier. Subjects with no assessments of PD will be censored at the time of first dose. Subjects who are lost to follow up for assessment of PD will be censored at their last tumor assessment or data cut-off date whichever is earlier. Kaplan-Meier methodology will be used to estimate median PFS for each cohort in Phase 1 and in each Arm in Phase 2.

The primary definition of PD for PFS is based on mRECIST. Analyses will be performed separately using objective disease responses definitions based on the mRECIST, RECIST v1.1, and GCIG CA-125 criteria. Analysis repeated for RECIST v1.1 and GCIG CA-125 are considered supportive.

10.2.1.3 Overall Survival

Duration of survival is defined as the time from first dose until date of death due to any cause. Subjects without documentation of death at the time of analysis will be censored as of the date the subject was last known to be alive. Kaplan-Meier methodology will be used to estimate the survival probabilities and median survival time for each cohort in Phase 1 and in each Arm in Phase 2.

10.2.1.4 Immune Biomarker Parameters

Changes in immune response parameters will be summarized using descriptive statistics by each cohort in Phase 1 and each Arm in Phase 2.

Tumor samples will be analyzed by multiplexed IHC to enumerate CD8/T_{reg} (FoxP3) ratio, biomarker expression, immune checkpoint expression including IDO, PD-L1 and tumor infiltrating lymphocytes. Plasma Kyn-Trp ratio, circulating tumor biomarkers, circulating cytokines and chemokines, circulating immune cell subsets and their activation status, listeriolysin (LLO) and mesothelin-specific T cells, and humoral responses against LLO, mesothelin, and other tumor antigens will be assessed.

10.2.2 Analysis of Safety

Safety assessments will occur on all subjects who received any study medication. All safety analyses will be performed for each cohort and overall in Phase 1 and each Arm and overall in Phase 2.

Terminations/premature withdrawals, adverse events, DLTs, vital signs, and laboratory data will be tabulated.

Terminations and premature withdrawals will be summarized by frequency counts and percentages.

Adverse events will be coded to a standard set of terms using the most current version of the Medical Dictionary for Regulatory Activities (MedDRA) dictionary and graded according to NCI CTCAE v4. Adverse events will be listed individually and incidence of adverse events summarized by system organ class and preferred terms within a system organ class. Analysis of toxicity will focus on SAEs and adverse events \geq Grade 3 and attribution to assigned therapy. Administration-site reactions will be listed and tabulated separately from the adverse events.

Changes in vital signs, hematology and clinical chemistry parameters from baseline to the end of the study will be examined. Treatment-emergent changes from normal to abnormal values in key laboratory parameters will be identified. Laboratory data will be summarized for each time point that specimens are collected. Changes in NCI toxicity grading of laboratory data will be presented using shift tables and listings of clinically significant values.

10.2.3 Interim Analysis

Safety data will be reviewed on an ongoing basis by the SRC.

For Phase 2 of the study, after 13 treated subjects are enrolled in an Arm (Stage 1), an additional 14 treated subjects will be enrolled in the Arm (Stage 2) if 1 or more subjects respond (objective disease response of CR or PR) or if the median PFS is at least 4.8 months. Objective response rate and PFS are based on mRECIST. If neither of the criteria for response and PFS is met, the preliminary anti-tumor activity in the Arm will be rejected and no further subjects will be randomized to the Arm.

10.2.4 Sample Size Determination

During Phase 1, dose escalation will be based on traditional escalation guidelines (3+3) to determine the RP2D and evaluate safety data (including DLTs and adverse events) of each planned treatment.

Phase 2 will be an open-label, randomized study design conducted in 2 stages to achieve up to 27 treated subjects per Arm. After 13 subjects in an Arm are randomized at the confirmed dose following the Safety Run-in (stage 1), an additional 14 subjects will be enrolled in that Arm (stage 2) if 1 or more subjects respond or if the median PFS is at least 4.8 months. If the criteria for either ORR or PFS are not met, the preliminary anti-tumor activity in the Arm will be rejected and no further subjects will be randomized to the Arm. If the Arm goes on to stage 2, a total of 27 treated subjects will be studied in that Arm. The Arm will be considered successful if 4 or more subjects respond or the median PFS is at least 4.8 months. If the criteria for either ORR or PFS are not met, the Arm will be rejected. This design is applied to each Arm independently. There are no formal comparisons planned between Arms.

This is an exploratory study of each Arm where the sample size and ORR and PFS criteria for each stage are based on clinical judgement; each Arm is assumed to be evaluated separately. Type I error will not be controlled over both Arms. The ORR criteria and number of subjects for each stage within Arm are based on a Simon minimax 2-stage design (null hypothesis that $ORR \leq 0.05$ versus the alternative that $ORR \geq 0.20$ with $\alpha = 0.05$ and $\text{power} = 0.80$). The PFS criteria are based on the lower limit of the 95% CI determined based on meta-analysis in the 3rd relapse patient population where the median PFS is 5.6 months, (95% CI: 4.8 to 6.2 months).⁶⁷ The one-sided test for PFS (i.e. observing median $PFS \geq 4.8$ months) has a Type I error rate of 0.0744 when the null hypothesis is that the median $PFS = 3.6$ months, PFS is exponentially distributed, accrual is uniform, and total study duration is 30 months for 27 subjects enrolled over 24 months. For a one-sided test of observing $PFS \geq 4.8$ months, there is approximately 77% power to detect a median PFS of 5.6 months and 50% power to detect a median PFS of 4.8 months.

Assuming a non-negative correlation between the one-sided tests for ORR and PFS, the overall Type I error for either test criteria being met is at most 0.1203. There is at least 70% power to meet at least one of the test criteria if $ORR = 0.25$ and median $PFS = 4.8$ and at least 79% power if $ORR = 0.25$ and median $PFS = 5.6$.

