3.4. Interim Analysis

Safety data will be reviewed on an ongoing basis by the SRC.

For Phase 2 of the study, after 13 subjects have been treated with the CRS-207 dose identified at the end of the Safety run-in period within an Arm (Stage 1), an additional 14 treated subjects will be enrolled in the Arm (Stage 2) if 1 or more subjects respond (objective disease response of CR or PR) or if the median PFS is at least 4.8 months. Objective response rate and PFS are based on mRECIST. If neither of the criteria for response and PFS is met, preliminary antitumor activity in the Arm has not been identified and no further subjects will be randomized to the Arm.

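### The arm-rejection sentences say 'either' where the design needs 'neither', so an arm meeting only one of the ORR and PFS criteria is both passed and rejected

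*Protocol*

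**What the plan says.** Protocol 10.2.4 states the rule for each arm twice, once per look, each time as a pass sentence followed by a rejection sentence.

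- **Stage 1, 13 subjects.** Fourteen more are enrolled "if 1 or more subjects respond or if the median PFS is at least 4.8 months". Then: "If the criteria for either ORR or PFS are not met, the preliminary anti-tumor activity in the Arm will be rejected".
- **Final, 27 subjects.** "The Arm will be considered successful if 4 or more subjects respond or the median PFS is at least 4.8 months". Then: "If the criteria for either ORR or PFS are not met, the Arm will be rejected".

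The Statistical Analyses part of the synopsis and SAP 3.3 carry the same two pairs, so the rejection wording occurs six times.

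The interim sections word the stage 1 stop differently. Protocol 10.2.3 has "If neither of the criteria for response and PFS is met, the preliminary anti-tumor activity in the Arm will be rejected", and SAP 3.4 has "If neither of the criteria for response and PFS is met, preliminary antitumor activity in the Arm has not been identified". Protocol 3.2 and SAP 3.1 also give the advancement criteria as one response or a median PFS of at least 4.8 months.

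The end of Protocol 10.2.4 and of SAP 3.3 gives the combined operating characteristics. Type I error for either criterion being met is at most 0.1203. Power to meet at least one is at least 70% (ORR 0.25, median PFS 4.8 months) or 79% (ORR 0.25, median PFS 5.6 months).

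**The concern.** The pass sentences are OR rules. The rejection sentences, taken literally, are AND rules, because failing one criterion is enough to reject. The two agree only when both criteria are met or both are missed.

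On a split result they give opposite answers. Suppose 1 of 13 subjects responds and median PFS is 4.1 months: one sentence enrols 14 more and the next closes the arm. Suppose the arm reaches 27 with fewer than four responses and a median PFS of 6.2 months: one sentence calls it successful and the next rejects it. These decide whether an arm goes on and whether it is declared active, and the two readings have very different error rates and power.

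**Working it through.** **1. Reproduce the plan's inputs.**

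*ORR.* An exact binomial search for the Simon minimax design (5% versus 20%, alpha 0.05, power 0.80) returns 0/13 and 3/27: continue at 1 or more, succeed at 4 or more. Its exact alpha is 0.0416 and its power 0.801. This is the plan's design.

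*PFS.* The plan assumes exponential PFS, 27 subjects, uniform accrual over 24 months and 30 months in total. With λ = ln 2 / median, the expected number of events is d = 27 × [1 − (e^(−6λ) − e^(−30λ)) / (24λ)]. The chance of an estimated median of at least 4.8 months is 1 − Φ(ln(4.8/median) × √d).

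| True median (months) | d | Computed | Plan |
|---|---|---|---|
| 3.6 | 25.18 | 0.0744 | 0.0744 |
| 4.8 | 23.83 | 0.500 | 50% |
| 5.6 | 22.90 | 0.770 | 77% |

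**2. Combine at the final look, under independence.**

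Type I error:
- OR: 1 − (1 − 0.0744)(1 − 0.0416) = 0.113.
- AND: 0.0744 × 0.0416 = 0.003. Under any correlation it cannot exceed the smaller of the two, 0.042.

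The plan's 0.1203 was not matched exactly; a nominal ORR alpha of 0.05 gives 0.1207. It holds as an upper bound for OR, and it is far from any AND value.

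Power at ORR 0.25, where the Simon design has power 0.922. The ranges run between independence and the limiting case (the larger of the two powers for OR, the smaller for AND):

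| Median PFS | OR | AND | Plan |
|---|---|---|---|
| 4.8 months | 0.92-0.96 | 0.46-0.50 | at least 70% |
| 5.6 months | 0.92-0.98 | 0.71-0.77 | at least 79% |

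The plan's power statements are true, though loose, for OR. They are false for AND.

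**3. How often the two sentences conflict at the final look.** Exactly one criterion is met with probability a(1 − b) + b(1 − a), under independence:
- Null: 0.0744 × 0.9584 + 0.0416 × 0.9256 = 0.11.
- ORR 0.25, PFS 4.8: 0.50 × 0.078 + 0.922 × 0.50 = 0.50.
- ORR 0.25, PFS 5.6: 0.77 × 0.078 + 0.922 × 0.23 = 0.27.

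**4. Both looks, by simulation.** This uses the Kaplan-Meier median named in Protocol 10.2.1.2, 13 then 27 subjects, the plan's accrual and study duration, and ORR independent of PFS. The stage 1 look is placed 6 months after the 13th entry; the documents give no timing, so that is an assumption. Ranges run from exactly observed PFS times to progression seen only at 9-weekly scans.

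- At ORR 25% and median PFS 5.6 months, success is about 0.97-0.99 under OR and about 0.51-0.67 under AND at both looks.
- At the null (ORR 5%, median PFS 3.6 months), success under AND at both looks is about 0.003-0.009.
- At the null, exactly one stage 1 criterion is met in about half of trials. The ORR part alone explains much of this: the chance of at least one response in 13 is 1 − 0.95^13 = 0.49.

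**The case against.** The strongest reply is that this is loose negation and not an open design question. Protocol 10.2.3 and SAP 3.4 are the sections devoted to the interim decision, and both stop only if neither criterion is met, so the example of 1 of 13 responding with a median of 4.1 months continues under them. The error and power statements are explicitly for at least one criterion, and the plan offers no AND figure. That stands. A reader might infer that it is impossible to tell which error rate applies; the documents do not support that, because only OR fits the stated 0.1203 and the stated power.

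It is also fair that little now depends on the rule. SAP 3.5 records the decision of 12 December 2017 to cease CRS-207 development. SAP 4 plans no significance test, SAP 7.1 keeps ORR out of the synopsis report, and SAP 9 lists efficacy without summarising it. No planned output applies the final rule.

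What the reply does not remove is that no passage restates the final rejection rule with 'neither'. The SAP, dated after the stop decision, still carries both wordings in adjacent sections as current text.

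**Conclusion.** Wrong as written: an internal inconsistency of lower severity. In the synopsis, Protocol 10.2.4 and SAP 3.3, the rejection sentences contradict the pass sentences at both looks. OR is the evident intent. The gap between the readings is large: Type I error 0.113 against 0.003 on the plan's inputs, and success of about 0.97-0.99 against 0.51-0.67 in simulation at ORR 25% and median PFS 5.6 months. The first pair assumes independence and applies AND only at the final look. The second also assumes the 6-month stage 1 delay and applies AND at both looks.

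Two stronger readings are tempting and should not be drawn.

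- *That the OR rule itself breaks the stated error bound.* The simulated null success rate under OR is above 0.12, but the excess comes from using a Kaplan-Meier median and from scan spacing, not from choosing OR over AND.
- *That 77% is the chance of success for an arm no better than history, so a PFS-only success needs a weaker label.* The 77% is a single-look parametric figure for the PFS criterion, not the arm's pass rate. The benchmark is a "meta-analysis in the 3rd relapse patient population where the median PFS is 5.6 months", which the documents do not describe as platinum-resistant, and they say the criteria rest on clinical judgement. Labelling such a result as PFS not below the historical lower limit would overclaim, since the rule passes half the time at a true median of 4.8 months. The unsourced 3.6-month null is a separate matter.

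**What to change.** In the synopsis (Statistical Analyses), Protocol 10.2.4 and SAP 3.3, change the opening condition of both rejection sentences, stage 1 and final, to: *If neither the ORR nor the PFS criterion is met*. That is six replacements. It brings the text into line with Protocol 10.2.3, SAP 3.4 and the stated error and power calculation.

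The thresholds, sample size and operating characteristics stay as they are. The cost is a wording correction, with no operational effect.
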